7.2 Qualitative Analysis

We will aim to interview carers until saturation of data is reached. We envisage this will be between 15-20 carers. Once we have achieved saturation we will cease inviting carers to take part in this component of the study. In qualitative studies robust data needs to be in-depth and a key method of assessing data quality is whether saturation is reached, where no new themes are being identified. A sample of 15-20 participants is likely to be adequate for data saturation and to provide a range of diverse views from carers representing a mix of gender, relationship and dementia severity (as described in Section 4.2).

Qualitative interviews will be audio-recorded on an encrypted digital recorder and then transcribed verbatim by the research team. Transcripts will be entered into NVivo qualitative software package (QSR International) to support data coding. This data will be thematically analysed [35, 36] by coding chunks of text and grouping these codes into themes and sub-themes that address the study objectives. Two researchers will independently code and analyse each interview independently and then compare codes and themes to ensure rigour in analysis. Discrepancies will be discussed until consensus on themes is reached. Interviews will be coded as collected to enable subsequent interviews to draw on and explore themes arising. While we aim to recruit carers from a mix of categories (gender, relationship type and dementia severity) we will not be able to make comparisons between groups because of the small numbers representing each group (eg there may be only one male son caring for someone with mild dementia). The themes identified will help to draw out individual experiences in relation to carer grief and access to supports to supplement and expand the quantitative data.

8 PATIENT AND PUBLIC INVOLVEMENT (PPI)

This study is one component of a fellowship study focusing on grief amongst family and friends caring for someone with dementia and the relationship between preparation for end of life and grief before death in dementia care. The full study has been reviewed by the Alzheimer's Society Research Network, which consists of people with dementia and family and friend carers. Seven Network members participated in a focus group to provide feedback on the study and expressed passionate views about the lack of information about dementia progression and end of life care and also the lack of service response to their grief throughout the trajectory of dementia. Written ratings were received from another 45 Network members in which two thirds rated the study between 1-4 on a priority rating from 1=highest priority to 10=lowest priority. Many provided positive feedback such as

"One effect on carers of people with dementia has often been described as a living bereavement, if this project can help to improve the type and level of appropriate support to carers then it will be very welcome."

"Important. There is a general reluctance to look ahead after a diagnosis of dementia, and the progression of the disease is not always explained clearly to carers."

"From my personal experience as a carer of a relative with dementia I suffered a more intense level of grief coming to terms with the fact that the person I cared for was not the person I knew and loved. It was at this point that my relative died to me, their actual death was a relief to me that their suffering had ended. This loss referred to as 'grief before death' is very real indeed and from personal experience there was little to no support apart from family members, to help me cope with my relative who no longer was the person I knew and loved."

Carers are also involved as monitors of the study and involved in the project Steering Group and an Expert by Experience Group reviewing all aspects of the study, reviewing analyses and providing suggestions for dissemination. Refer to the 'Monitoring and Auditing' Section of this document for the research governance structure for this study which incorporates input from carers.

9 FUNDING AND SUPPLY OF EQUIPMENT

The study funding has been reviewed by the UCL/UCLH Research Office, and deemed sufficient to cover the requirements of the study. The research costs for the study have been supported by an Alzheimer's Society Senior Research Fellowship, Grant Reference number 325 (AS-SF-16-004), Funding: £300,662 (1/4/2017-31/3/2020). The funding covers costs of a computer for the CI, a computer for the Research Assistant and an encrypted digital recorder for the study all located at UCL. Contracting costs for Dementia UK to support recruitment of carers and Admiral Nurses are also included in the budget. Admiral Nurses will be recruited for another element of this study which will have a separate protocol and ethics application. Mail out and postage costs incurred by services distributing expression of interest letters have been included in the grant budget.

10 DATA HANDLING AND MANAGEMENT

Questionnaires will be collected on a paper based Case Report Form (CRF) (See Appendix 1 [CRF] and Appendix 2 [HLQ]). The HLQ may be self-completed by the carer prior to the face-to-face interview and collected by the researcher at the time of the interview. The CRF will be completed at the interview by the researchers at a location selected by the participants (most likely in their own homes). The CRF and HLQ will be returned by the researcher to UCL and locked in a filing cabinet in the secure UCL offices.

The subsample of 20 carers taking part in the semi-structured interviews will be asked to provide consent for audio-recording the interview using an encrypted digital recorder. The encrypted recorder requires a 4 digit PIN to be entered to turn it on. Listening to any recordings also requires entering another password. If participants consent to be audio recorded the researcher will download the audio-recording to a secure University College London (UCL) computer as soon as feasible after completing the interview. Once downloaded it will be deleted from the digital recorder. If they do not consent to be audio-recorded, the researcher will take written notes from the interview. Audio-recordings and written notes will be transcribed verbatim by the research team and saved on secure UCL computers.

All paper documents (HLQ, CRF, and semi-structured interview notes) for the study will be stored in accordance with the Declaration of Helsinki. All the information will be kept strictly confidential and held in accordance with the principles of the Data Protection Act (1998). Each participant will be assigned a research number and all data will be stored without subject name or address or date of birth. Data will be held on a secure database on a password-protected computer in the Marie Curie Palliative Care Research Department, Division of Psychiatry, [name], UCL. Access to data will be restricted to appropriate members of the research team.

As per the research governance framework overseeing the study (See diagram in the 'Monitoring and Auditing' section), the Data monitoring and research ethics team will review and oversee all data collection and monitoring procedures.

11 PEER AND REGULATORY REVIEW

The study has been peer reviewed in accordance with the requirements outlined by UCL. The study was presented at workshops and seminars within UCL and received feedback from attendees. The CI received input into the design from [name], previous head of the MCPCRD, the MCPCRD statistician and [name], joint director of the Priment Clinical Trials Unit and joint lead on the UCL arm of the London Research Design Service. After this input the study was successfully awarded funding by the Alzheimer's Society in an open competitive grant scheme.

The Sponsor considers the procedure for obtaining funding from Alzheimer's Society to be of sufficient rigour and independence to be considered an adequate peer review.

12 ASSESSMENT AND MANAGEMENT OF RISK

12.1 Assessment and management of risk to participants

The interview covers topics about future planning and plans for end of life care as well as loss and grief during caring for someone with dementia. These are sensitive topics that may arouse an emotional response from participants. We have developed a procedure to minimise and respond to any participant who becomes distressed. The procedure draws on the framework for ethical-decision making that has been developed in the UK for research with bereaved family and carers [37] and which are mostly applicable to this study.

Prior to the interview, participants will be informed that the interview may be emotional and tiring and to think about and agree on avenues of post-interview support. Prior to the interview, participants will also be asked to make the interviewer aware if they want to pause the recording. This will also be offered to carers who appear upset or appear to be tiring during the interview. They will be offered a break, to postpone the interview or to withdraw their participation. At the end of the interview carers will receive information on local carer support agencies and if they are experiencing distress will be advised to contact their GP or Alzheimer's Society National Dementia Helpline. We will facilitate this

process if necessary. We have also included three questions from the above mentioned framework at the end of the CRF [37]:

- Do you feel you could cope with the length of the interview?
- Did you find talking in the interview helpful?
- Did you feel the interview caused you distress?

These questions will enable us to monitor the impact of the study. Sque et al [37] in their sample of bereaved carers (n=31) found that 90% could easily cope with the length of the interview, most found it very helpful (81%) or a little helpful (16%) and 58% found it a little distressing with only 3% reporting it caused a lot of distress. We will revise the protocol if we are finding that this study is causing greater distress and burden and is unhelpful. We will call participants two days later to check whether thinking about the interview has raised any concerns or questions for them.

In our extensive experience of undertaking interviews with carers of people with dementia and addressing topics such as grief, loss and end of life care, we find that interviews can provide a cathartic experience for carers, providing them an opportunity to talk about their thoughts and feelings to an impartial researcher who is disconnected to their personal social network. Death and end of life care are topics that tend to be avoided in society and yet impact all of us. Providing an avenue to talk about some of these issues can be welcomed by participants who have not had an opportunity to express these thoughts before. Family carers may be motivated to participate to educate others about their experiences of care to help improve services and to be able to talk about issues they haven't previously had an opportunity to discuss. The benefits of learning about the process of grief and how we can improve supports to carers is an important area of research with the growing number of people living with dementia and as dementia is now the largest cause of death in the UK [1].

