4.1 Quantitative interviews (n=150)

The study will aim to recruit 150 carers over a 15 month period starting in late 2017. The recruitment and consent process is described in detail in Section 6 and the power calculation in Section 7. Carers will provide written, informed consent before completing a face-to-face interview in a location of their choice. Previous experience in research with carers indicates that the majority will wish to be interviewed in their own home or the home of the person with dementia. Researchers will undertake the interview in pairs to begin with but on their own after training is complete. They will adhere to the UCL lone worker policy.

Researchers will ask questions and record answers on the Case Report Form (Appendix 1). The CRF contains demographic questions about the carer and some basic information about the person with dementia (such as dementia severity, type of diagnosis and time since diagnosis).

The Marwit-Meuser Caregiver Grief Inventory Short Form (MMCGI-SF) [25] will be used to assess severity of grief before death. This scale contains three subscales: heartfelt sadness and longing, worry and felt isolation, and personal sacrifice burden; a cutoff of 70/90 is considered a high level of grief.[25] The Clinical Dementia Rating scale will assess dementia severity based on the carer's report [26]. To test the primary hypothesis we will collect a number of measures to reflect the five modifiable factors that suggest preparation for end of life:

1. Greater knowledge of how dementia progresses (Dementia Knowledge Assessment Scale [27])
2. Greater knowledge of the person with dementia's end of life preferences (Discussed wishes regarding end of life with your relative? Have a good understanding of their wishes for end of life care?)
3. Having a lasting Power of Attorney or other formal advance directives in place - a proxy indication of "preparedness" (binary variable; any form of directive in place/not in place)
4. Higher satisfaction with communication with healthcare providers (Health Literacy Questionnaire [HLQ, excluding Social Support subscale] which examines how well carers understand health information and navigate the health system [28]) (See Appendix 2)
5. Higher satisfaction with support for health from social network (HLQ-Social Support subscale.[28])

A number of other measures have been included for other exploratory analysis and to control for possible confounders. These include:

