15 TRAINING

The CI will review and provide assurances of the training and experience of all staff working on this study. Appropriate training records will be maintained in the study files. The CI will complete UCL core training requirements supervising staff as well as statistical courses on regression and statistics for health research (statistics will also be overseen by the study's statistician [name]). Other compulsory training for researchers involved in the study will include Good Clinical Practice and SLMS Information Governance annual training.

Interviews will be undertaken by the CI and the Research Assistant who will be employed. The CI has a psychology and social science background and extensive research experience in undertaking interviews with carers of people with dementia across all stages of dementia progression. The Research Assistant will be employed at a level 6B and will have research experience and a degree relevant to mental health and dementia care. The Research Assistant will be provided with training

from the CI to conduct the interviews. The Research Assistant will observe the CI complete 1-2 interviews. When they feel confident to complete the interview they will complete the interview under observation from the CI. It is envisaged that they will be observed for 2-3 interviews until they feel confident and the CI feels they have achieved the level of competency required for completing the interviews. This training process will also involve debriefing sessions and reflection on the topic and nature of the interviews. After the initial training period, the research assistant will also have regular debriefing sessions with the CI as well as any additional sessions if the research assistant feels they need it. They will ring or meet with the CI directly after any interviews they have found distressing.

Additional clinical support to the CI and Research Assistant will be provided by the fellowship supervisor [name] and co-supervisor [name], both experienced, internationally renowned dementia and end of life care researchers and Old Age Psychiatrists.

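### Carers rate the interview's length, helpfulness and distress to the person who conducted it, which may understate distress in the only measure tied to the protocol-revision commitment

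*Combined protocol and SAP*

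**What the plan says.** Section 12.1 recognises that the topics are sensitive and adds three items on whether the carer coped with the length, found the interview helpful and was distressed by it: "We have also included three questions from the above mentioned framework at the end of the CRF". Their purpose is explicit: "These questions will enable us to monitor the impact of the study". After citing results from 31 bereaved carers, the section makes a commitment: "We will revise the protocol if we are finding that this study is causing greater distress and burden and is unhelpful".

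The mode of asking is set elsewhere. Section 4.1: "Researchers will ask questions and record answers on the Case Report Form (Appendix 1". Section 10: "The CRF will be completed at the interview by the researchers at a location selected by the participants", which it expects to be mostly carers' own homes. Section 15: "Interviews will be undertaken by the CI and the Research Assistant who will be employed". Section 4.1 adds that researchers work in pairs at first and alone once trained.

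One instrument has a different route. Section 10: "The HLQ may be self-completed by the carer prior to the face-to-face interview". No such route is described for the three items.

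**The concern.** A carer who found the interview upsetting or unhelpful has to say so aloud to the interviewer, who then records the answer. That interviewer is either the CI or the Research Assistant whom the CI trains. Politeness in this setting would most plausibly soften criticism rather than sharpen it. The likely error is therefore one-sided: reported distress too low, reported helpfulness and coping too high.

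The same direction makes the Section 12.1 commitment less likely to be acted on. The study could conclude that its grief interview was well tolerated partly because of how the question was put. At stake is a participant-protection commitment, not the main scientific result.

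**Working it through.** **1. Who asks and records the items.** Section 12.1 places them on the CRF. Section 4.1 has the researcher ask and record CRF questions, and Section 10 has the researchers complete the CRF at the interview. Section 15 limits interviewers to two people. Read together, the rated person collects the rating. The only questionnaire with a self-completed option is the HLQ, and the three items are not part of it.

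**2. What the items decide.** In Section 12.1 the revision commitment follows directly from these items and the cited percentages. It gives no numerical threshold, time of review or named reviewer. The summary after 50 carers in Section 6.1.4 covers the mix of carers (dementia severity, gender, relationship, deprivation), not distress.

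**3. The cited comparison figures.** Each percentage in Section 12.1 corresponds to one whole count out of 31:

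- coped easily with the length: 28/31 = 90.3% (stated 90%)
- very helpful: 25/31 = 80.6% (stated 81%)
- a little helpful: 5/31 = 16.1% (stated 16%)
- a little distressing: 18/31 = 58.1% (stated 58%)
- a lot of distress: 1/31 = 3.2% (stated 3%)

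The figures reproduce. The last one is a single person, with an exact (Clopper-Pearson) 95% interval of 0.1% to 16.7%. It is an imprecise yardstick under any mode of asking.

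**4. Direction of the possible error.** Let p be the true share of carers who were much distressed, and u the share of those who give a milder answer face to face. Assume that nobody overstates distress to the interviewer. The expected recorded share is p(1 − u), which is below p whenever u > 0. The documents give neither p nor u. For scale only, with an assumed p of 10%:

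- u = 0: 10% × 1.00 = 10%
- u = 25%: 10% × 0.75 = 7.5%
- u = 50%: 10% × 0.50 = 5%

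The same reasoning applies to carers who found the interview unhelpful.

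**5. Effect on the comparison.** Let p₀ and u₀ be the same quantities in the 31-person sample. The recorded ratio is p(1 − u) / [p₀(1 − u₀)]. If u = u₀, the ratio is p/p₀ and the bias cancels in relative terms, although the absolute gap still shrinks by the factor (1 − u). The protocol does not say how that sample was asked, so u₀ is unknown too.

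**6. What is not calculated.** The chance that a real problem would be missed depends on a trigger, and the protocol states none. Any such probability would describe an invented rule, so none is given.

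**The case against.** A reader might infer that these items are the study's only safety signal. The documents do not support that. Section 12.1 also promises every participant a telephone call two days later and has interviewers respond to carers who seem upset. Sections 13.6 and 13.7 cover adverse event recording and SAE reporting to the sponsor. Sections 10 and 14 describe a data monitoring and research ethics group, and Section 8 involves carers as monitors. All of this stands. None of it is tied to the revision commitment, however. No caller, record or tabulation is stated for the call, which the interviewer could make. Section 13.1 anticipates no adverse events. No passage gives the oversight group independently collected distress data.

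A reader might also infer that courtesy bias is established. It is not: the documents show neither its presence nor its size, so *may understate* is as far as they go.

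The comparison argument also has force. If the cited sample was asked face to face, some of the bias is shared, and a private slip would create a mismatch of mode. But because that mode is not stated, comparability is uncertain whichever way this study asks.

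Finally, a spoken answer is available at once, while a sealed one is not, and a slip carrying a research number is not anonymous to a small team. The first is met by keeping a spoken check at the visit. The second means that the slip would reduce the pressure to be polite, not remove it.

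**Conclusion.** The point holds as a modest design weakness. The items behind the revision commitment are collected by the person being rated, no private route is described, and any resulting error would most plausibly make revision less likely. Its size cannot be determined from the documents.

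The conclusion assumes that the CRF is administered as Sections 4.1 and 10 describe. Appendix 1 was not available for review, so an instruction on the form itself to self-complete these items cannot be excluded. It also assumes that carers soften criticism in front of the interviewer more often than they exaggerate it.

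The primary MMCGI-SF analysis in Section 7.1 is not affected. The change is worth making because it costs almost nothing, not because harm has been shown.

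**What to change.** Move the three items, with whatever response options the CRF already carries, to a one-page slip identified only by research number. The carer completes it privately and seals it in an envelope before the researcher leaves. It is read at UCL before the two-day call, and the running tabulation goes to the existing data monitoring and research ethics group. If a slip has to be read aloud to a carer, record that on it.

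Keep the interviewer's spoken check at the end of the visit and every existing support step in Section 12.1 exactly as they are; the slip supplies the tabulated figures only. When results are set against the 31-person sample, state that its mode of asking is not given.

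The cost is one printed page and one envelope per carer (150 of each at full recruitment), plus a sentence each in Sections 4.1 and 12.1, with no extra visit or staff. There are two downsides: the written answers are read after the visit rather than during it, and comparability with the cited sample may change.

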12.2 Assessment and management of risk to research staff

Research staff undertaking interviews within participants' homes also face potential risks. Research staff will follow the following procedures to try to identify, minimise and manage risks following the UCL's lone worker policy.

